### 11.6 Safety Analyses

Safety analyses will be provided for the Double-Blind safety and open-label safety populations. All safety data will be listed and summarized. No formal statistics will be performed for the safety analyses.

For the Double-Blind Treatment Phase, summaries will be presented by treatment arms. For the OLE Phase, results will be tabulated by treatment received during the Double-Blind Treatment Phase (including active arms pooled) and overall.

#### 11.6.1 Adverse Events

An AE is defined as any untoward medical occurrence associated with the use of a drug in humans, whether or not considered drug related.

A treatment-emergent AE (TEAE) is

- any AE reported after the first dose of study drug and up to 30 days after last dose of study drug, or
- any worsening of a pre-existing condition reported after first dose of study drug and up to 30 days after last dose of study drug.

For the OLE Phase, any AE starting on or after the first dose of OLE treatment will be considered treatment emergent.

A serious AE (SAE) is defined as any AE that results in any of the following outcomes: death, is life-threatening, results in inpatient hospitalization or prolongation of existing hospitalization, results in a persistent or significant incapacity or substantial disruption of the ability to conduct normal activities of daily living or is a congenital anomaly/birth defect. Important medical events that may not result in death, be life-threatening, or require hospitalization may be considered SAEs when, based upon appropriate medical judgment, they may jeopardize the patient and may require medical or surgical intervention to prevent one of the outcomes listed in this definition.

---

An AE's relationship to study treatment will be evaluated by the Investigator. The following relationships will be collected in eCRF: definitely related, probably related, possibly related, unlikely related, or not related. AEs that are evaluated as definitely, probably, or possibly related (or with missing relationship) will be considered treatment-related AEs for summary purposes.

The severity of AEs will be classified by the Investigator as mild, moderate, or severe. If the severity is missing, the AE will be assumed to be severe.

An overall TEAE summary will be generated presenting the frequency and percentage of patients and the number of AEs for the following:

- Any TEAE
- Any treatment-related TEAE
- Any severe TEAE
- Any treatment-related severe TEAE
- Any serious TEAE
- Any treatment-related serious TAE
- Any TEAE leading to study discontinuation
- Any TEAE leading to discontinuation of investigational product (IP)
- Any TEAE leading to interruption of IP
- Any TEAE leading to death

All AEs will be coded using MedDRA; the version used will be included in the tables and listings footnotes. The TEAEs will also be summarized by system organ class (SOC) and preferred term (PT), by severity and relationship to study treatment.

The TEAE summary tables will be sorted by SOC and PT. SOC's will be displayed in descending order of overall frequency in the pooled pitolisant group and then alphabetically. PTs will be displayed in descending order of overall frequency and then alphabetically within SOC. A patient with 2 or more events within the same PT of summarization will be counted only once in that level using the most severe incident or most related incident. Percentages will be based on the number of patients in the safety population. The following summaries by SOC and PT will be provided:

- TEAE
- Treatment-related TEAE
- TEAE by maximum severity
- Serious TEAE
- Treatment-related serious TEAE
- TEAE leading to discontinuation of IP
- TEAE leading to interruption of IP
- TEAE leading to death

Finally, a summary of all AEs and all SAEs by SOC and PT will be provided.

All AEs will be presented in a data listing. Separate data listings will be generated for treatment related AEs, SAEs, and AEs leading to study discontinuation.

For patients who opt to continue in the OLE Phase of the study, only AEs started on or before the last dose of the Double-Blind Treatment Phase will be included in the summaries for the Double-Blind Treatment Phase. AEs started after the last dose of treatment and up to 30 days after the last dose of treatment in the Double-Blind Treatment Phase will be included in a separate listing and summarized in the OLE Phase reporting.

For clinicaltrials.gov and other registries, the following will be produced in XML format.

1. All-Cause Mortality: \*§ A table of *all* anticipated and unanticipated deaths due to any cause, with the number and frequency of such events by arm or comparison group of the clinical study.
2. Serious Treatment-Emergent Adverse Events: \* A table of *all* serious adverse events, grouped by System Organ Class, with the number and frequency of such events by arm or comparison group of the clinical study.
3. Other (Not Including Serious) Treatment-Emergent Adverse Events: \* A table of anticipated and unanticipated events (not included in the serious adverse event table) that exceed a frequency threshold (for example, 5 percent) within any arm of the clinical study, grouped by organ system, with the number and frequency of such events by arm or comparison group of the clinical study.

XML schema are here: <https://prsinfo.clinicaltrials.gov/RRSUploadSchema.xsd>

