# 8.3. Time Period and Frequency for Adverse Event Assessment and Follow-up

### 8.3.1. Adverse Event and Serious Adverse Event Monitoring

All AEs regardless of seriousness, severity, or causality will be collected from the time the patient provides written informed consent through 30 (+3) days after final dose of study drug (Safety Follow-up TCs, Section 7.4).

For patients who receive study drug in the Double-Blind Treatment Phase and do not enter the OLE Phase of the study, if an Investigator becomes aware of an SAE that occurs at any time after the patient's study participation and the Investigator considers the event to be possibly related to the study drug, the Investigator should report the SAE to the Sponsor as described in Section 8.4.1.

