### 9.4.3. Safety Analysis

All safety analyses will be completed for the double-blind safety and open-label safety populations. All safety data will be tabulated or listed. No formal statistics will be performed for the safety analysis.

Adverse events that occur between the time written informed consent is provided and the start of study drug administration will be considered pretreatment AEs. Adverse events that start during or after study drug administration, or AEs with an onset prior to study drug administration that worsen after study drug administration will be considered TEAEs. All TEAEs will be coded and tabulated by System Organ Class and Preferred Term. Incidence of TEAEs and SAEs will be summarized. Adverse events leading to study withdrawal, if any, will be listed separately. Adverse events will be summarized with counts and percentages.

Laboratory parameters will be summarized. For each laboratory test, individual patient values will be listed and values outside of the standard reference range will be flagged. Shift tables will be produced showing the frequency of shifts from Baseline to the lowest and to the highest on study value in and out of the normal range as well as by visit. Laboratory parameters will also be summarized by visit.

The change from Baseline to each visit for vital sign variables will be summarized. Abnormal vital sign values will be flagged and listed. ECG and Holter monitor abnormalities, cardiac arrhythmias and other categorical outcomes will be summarized with counts and percentages. Continuous outcomes will be reported using summary statistics. Results of C-SSRS will be listed.

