## 9.4 Double-Blind and OLE Analyses Reporting

The data collected for the Double-Blind Treatment Phase and the OLE Phase are included in the same database.

A data cut will be performed at the end of the Double-Blind Treatment Phase and another one will be performed at the end of the OLE Phase. The date of first dose in the OLE Phase will be used to determine if a patient entered the OLE Phase. A data cut-off will be applied to the datasets and only data related to the Double-Blind Treatment Phase will be reported:

- Baseline and baseline characteristics.
- Visits performed in the Double-Blind Treatment Phase, up to and including Visit 5 (Week 11) for patients who entered the OLE Phase, and up to the safety follow-up visits for patients who opt out of the OLE Phase.
- For patients who entered the OLE Phase, any adverse event (AE) or medication that started up to and including the last dose of study drug in the Double-Blind Treatment Phase. For this patient group a (any AE or medication that started after and up to 30 days after the last dose of study drug in the Double-Blind Treatment Phase will be reported in separate listings, i.e., they will be excluded from the Double-Blind Treatment Phase summary tables).
- For patients who opt out of the OLE Phase, all AEs and medications reported through the final 30-day safety follow-up telephone contact will be reported as part of the Double-Blind Treatment Phase.

The date of first dose in the OLE Phase will be kept in the datasets to determine if the patient has entered the OLE Phase.

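### The SAP defines a treatment-emergent AE by when it is reported, which conflicts with the protocol's onset rule and the SAP's own start-date rules and can misflag events at either end of treatment

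*SAP*

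**What the plan says.** SAP 11.6.1 gives a two-part TEAE definition. The first part is "any AE reported after the first dose of study drug and up to 30 days after last dose of study drug, or" and the second is "any worsening of a pre-existing condition reported after first dose of study drug and up to 30 days after last dose of study drug". Both depend on when something is reported.

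The next sentence of the same section sets the OLE rule on a different basis: "any AE starting on or after the first dose of OLE treatment will be considered treatment emergent".

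Protocol 9.4.3 uses onset. TEAEs are "Adverse events that start during or after study drug administration, or AEs with an onset prior to study drug administration that worsen" after dosing. Events between consent and the "start of study drug administration will be considered pretreatment AEs". The protocol rule has no upper time limit.

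Two other passages fix the timing at the late end. Protocol 8.3.1 collects AEs from when the patient "provides written informed consent through 30 (+3) days after final dose of study drug". For patients who opt out of the OLE, SAP 9.4 says "all AEs and medications reported through the final 30-day safety follow-up telephone contact will be reported as part of the Double-Blind Treatment Phase".

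SAP section 6 states that the SAP governs where the two documents differ and that substantive changes from the protocol will be described. SAP 6.1 lists the changes; the TEAE definition is not among them.

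**The concern.** The date an event begins and the date the site hears of it can differ by days or weeks, particularly where contact is by scheduled telephone call. A definition based on the second date can put an event on the wrong side of either boundary.

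Two programmers, one following SAP 11.6.1 to the letter and one following protocol 9.4.3, could produce different TEAE tables from the same data. Most of the detailed safety output depends on this flag: related, severe, serious, leading to discontinuation or interruption, the tables by system organ class and preferred term, and the serious and other adverse event tables prepared for registries. The final call is also where the protocol asks specifically about arrhythmia symptoms, syncope and psychiatric events, so late-reported events deserve a clear rule.

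**Working it through.** The plan gives no figure to reproduce. The check is to classify example events under both rules.

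**Inputs**
- First dose is Day 1 and last double-blind dose is Day 77 (protocol 3.1.1.2).
- AEs are reviewed at the Baseline Visit. Its window is Day -3 to Day -1, and protocol 7.2.1 places the assessments on Day -1.
- The next scheduled AE contact is TC 1, Day 8 ±3 (protocol 7.2.3).
- Follow-up calls come 15 (±3) and 30 (+3) days after last dose (protocol 7.4). The final call may therefore fall on days 30 to 33, which is Day 107 to Day 110 here.
- Literal SAP rule: report after first dose and no later than 77 + 30 = Day 107.
- Protocol rule: onset on or after first dose, or worsening after it.

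**Classification**

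| Event | First reported | SAP, literal | Protocol |
|---|---|---|---|
| Onset Day -1, after the Baseline review | TC 1, Day 8 | TEAE | Pretreatment |
| Onset last dose + 25 (Day 102) | Final call, day 30 (Day 107) | TEAE | TEAE |
| Same onset | Final call, day 31 (Day 108) | Not a TEAE | TEAE |
| Same onset | Final call, day 32 (Day 109) | Not a TEAE | TEAE |
| Same onset | Final call, day 33 (Day 110) | Not a TEAE | TEAE |
| Onset last dose + 31 (Day 108) | Final call, day 33 (Day 110) | Not a TEAE | TEAE |

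Rows 3 to 5 show one event changing status according to which permitted day the site telephones. The last row shows that the SAP's 30-day limit also differs from the protocol, apart from the wording about reporting.

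**Who can be affected late.** In the double-blind tables this arises only in patients who do not enter the OLE. For those who do, SAP 9.4 and 11.6.1 cut the double-blind summaries by start date at the last double-blind dose. The OLE TEAE rule has no upper limit.

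**Effect on a table.** About 30 patients randomized 1:1:1 gives 30 / 3 = 10 per arm. One patient is 1 / 10 = 10 percentage points of a row. SAP 11.6.1 counts a patient once per preferred term, so the row moves only if the misflagged event is that patient's only TEAE in it. A patient who already has another TEAE does not change the any-TEAE row.

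**The case against.** The strongest reply is that *reported* is loose wording for *occurring*. The SAP works on start dates elsewhere: the OLE rule, the phase cuts in 9.4 and 11.6.1, and the start-date imputation table in Appendix 5. The documents describe no report-date variable and no way to impute one. SAP 6.1 declares no change, which fits a slip better than a deliberate new rule. SAP 9.4 also calls the last contact the 30-day follow-up call, so the 30-day limit may have been meant to run through that call. This reading is plausible. But no passage overrides the literal definition, and if it is a slip, the correction is the same.

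The cases are also narrow, and that stands. The early one needs an onset in the short gap between the Baseline review and first dose, or an event the patient did not mention at Baseline. The late one needs a patient outside the OLE, no earlier report at the first follow-up call or an unscheduled contact, and a final call after day 30.

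A reader might infer four stronger things that the documents do not support:
- *That most events first reported at the final call drop out.* Three of the four days in a 30 (+3) window are past day 30, but a 75% loss would need calls spread evenly, for which there are no data. The synopsis safety section and protocol 3.1.1.3 and 4.4.3 print the window as 30 (±3), possibly a PDF-reading artefact. On that reading the call can precede day 30, and 3 of 7 permitted days (43%) are late.
- *That these events vanish from the report.* SAP 11.6.1 also provides a summary of all AEs and all SAEs and a listing of all AEs, and SAP 9.4 keeps them in the double-blind report. Only the TEAE flag is affected.
- *That the loss falls on the patients with most tolerability problems.* No passage shows this for early stoppers or OLE decliners.
- *That every misflagged patient shifts an incidence by 10 points.* The once-per-patient count prevents this.

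**Conclusion.** The point holds as a conflict of definition that should be corrected. The literal rule in SAP 11.6.1 differs from protocol 9.4.3 and from the SAP's own use of start dates, and the difference is undeclared. It can add a pretreatment event to the TEAE tables, and it can remove the TEAE flag from a follow-up event according to the day of a permitted call.

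The effect is confined to the TEAE and TEAE-based registry tables. The number of events affected cannot be computed from the documents. The per-patient effect, about 10 points in a row, assumes about 10 patients per arm and no other TEAE for that patient in that row. The late case assumes a final call on days 31 to 33, which both printed versions of the window allow.

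**What to change.** In both limbs of SAP 11.6.1, replace the report date by onset. Suggested wording: *any AE with onset date (imputed per Appendix 5) on or after first dose, or any pre-existing condition whose worsening began on or after first dose, through the end of the AE collection window (30 +3 days after last dose), irrespective of the date reported.* This puts both phases on the same basis and matches the upper limit to protocol 8.3.1.

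If the sponsor prefers a strict 30-day onset limit, keep it but declare it in SAP 6.1 as a change from protocol 9.4.3, which has none. The printed versions of the final-call window, (+3) and (±3), should be checked against each other at the same time.

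The cost is SAP wording only. AE start dates and their imputation rules are already provided for, and no new data or procedures are needed.

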## 9.2 Study Day Windows

For each patient there will be a screening period, a Double-Blind Treatment Phase, and an optional OLE Phase.

The study day for data collected after the first dose of study drug will be calculated as visit/assessment date – first dose date + 1. For data collected prior to first dose, the study day will be calculated as visit/assessment date – first dose date. The first dose date refers to the date the study drug was taken for the first time, i.e., at the beginning of the Double-Blind Treatment Phase.

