### **OLE Phase:**

For reporting the OLE analyses, no data cut-off will be applied to the datasets. Only data related to the OLE Phase will be reported:

- Demographics and baseline characteristics for patients who received at least one dose of study drug within the OLE Phase
- Baseline safety and efficacy data ([section 9.3](#))
- Safety and efficacy reported during the OLE Phase
- AEs and concomitant medications started on or after the 1st dose of OLE study drug intake

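### The open-label extension (OLE) rule for treatment-emergent events goes by start date alone, so an earlier event that worsens on open-label pitolisant under its original date is missing from the OLE summary tables

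*SAP*

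**What the plan says.** SAP 11.6.1 defines a treatment-emergent AE by two limbs. One is an AE reported after the first dose of study drug. The other is "any worsening of a pre-existing condition reported after first dose of study drug and up to 30 days after last dose of study drug". A separate sentence for the OLE follows: "any AE starting on or after the first dose of OLE treatment will be considered treatment emergent". It has no worsening limb.

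SAP 9.4 sets the scope of the OLE report: "Only data related to the OLE Phase will be reported". The AE item under it covers "AEs and concomitant medications started on or after the" first OLE dose.

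For patients who continue into the OLE, SAP 11.6.1 governs the double-blind tables as follows: "only AEs started on or before the last dose of the Double-Blind Treatment Phase will be included in the summaries". AEs that start after the last double-blind dose, up to 30 days, are listed separately and summarized with the OLE.

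Protocol 9.4.3 applies the safety analyses to both the double-blind and the open-label safety populations. It also has a worsening limb: "AEs with an onset prior to study drug administration that worsen after study drug administration will be considered TEAEs".

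**The concern.** A treatment-emergent definition is meant to catch both new events and existing events that get worse after exposure. The OLE rule keeps the first and drops the second. The OLE is where this matters most. Ex-placebo patients take pitolisant for the first time there, and lower-dose patients may go from 17.8 mg to 35.6 mg. Long-term safety is a secondary objective, and SAP 11.6 plans OLE safety tables by double-blind treatment group as well as overall.

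The start-date filter also feeds the OLE tables by maximum severity, of serious events, and of events leading to interruption or discontinuation of study drug. A mild AE that began in the double-blind phase, became severe on open-label drug and ended treatment could be absent from all of them. Both documents say that the SAP prevails where it differs from the protocol, so the SAP wording is what would be programmed.

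**Working it through.** There is no figure in the plan to reproduce; the check is to run cases through the rules. The days are illustrative. The last double-blind dose is taken as Day 77 and the first OLE dose as Day 78, as scheduled. Each AE is assumed to be one record with its original start date.

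| Case | OLE tables (SAP 11.6.1 and 9.4) | Double-blind tables (SAP 11.6.1) | Protocol 9.4.3 |
|---|---|---|---|
| A. Mild from Day 60 on placebo, severe on Day 100 | Excluded: Day 60 is before Day 78 | Included: Day 60 is not after Day 77, so counted under placebo | Already treatment-emergent; no rule for re-emergence in the OLE |
| B. Begins in screening, stable through Day 77, first worsens on Day 100 | Excluded: start is before Day 78 | Start date qualifies, but it did not worsen in that phase | Treatment-emergent, because it worsened after study drug |
| C. Begins after the last double-blind dose but before the first OLE dose | Included, by the specific rule in SAP 11.6.1 | Separate listing only | Treatment-emergent |

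Case A: the double-blind tables show the AE as mild if the data cut precedes the worsening. If the record is updated before the cut, they show it as severe under placebo. The second outcome is possible because Protocol 9.4.2.1 allows the double-blind analysis while patients are still in the OLE. Neither outcome shows a worsening on open-label pitolisant.

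Case B: AEs are collected from consent (Protocol 8.3.1), so this case can arise. The AE is either in no treatment-emergent table or is placed in the phase in which it did not worsen. The summary of all AEs by system organ class and preferred term would still hold it on the double-blind side.

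Case C shows that the OLE tables are not strictly confined to AEs from the first OLE dose onward. It does not help A or B, whose onset is earlier.

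Does the general worsening limb rescue A and B? Its reference point is the first dose of study drug. In SAP 9.2, "The first dose date refers to the date the study drug was taken for the first time", that is, at the start of the double-blind phase. An AE with onset after that date is not clearly a pre-existing condition, so A is doubtful. B does satisfy the limb, but it would still have to pass the start-date filter in SAP 9.4, and it does not.

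Scale of one missed patient, assuming that all 30 planned patients enter the OLE in equal groups of 10:

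- overall: 1/30 = 3.3%
- ex-placebo group: 1/10 = 10%

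The OLE is optional. With fewer entrants, each missed patient is a larger share. The documents give no basis for estimating how many there would be.

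**The case against.** The strongest answer is that the loss depends on a recording convention that the documents do not state. Protocol 8.1.1 gives the exacerbation of a pre-existing condition as an example of an AE, and Protocol 6.3.6 has worsening seizures reported as AEs. If each worsening is entered as a new AE, its start date falls in the OLE and the present rule captures it. This stands as a condition. It does not settle the matter: Protocol 8.3.2 has ongoing AEs reviewed at later contacts, which fits a single continuing record equally well, and the eCRF is not among the documents.

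It can also be said that the general definition is not expressly displaced, and that SAP 9.4 has a broader item for safety data reported during the OLE. That is fair. But the item specific to AEs selects by start date, and no text brings an earlier-onset AE into the OLE tables.

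Three stronger readings are tempting, and the documents do not support them.

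- A reader might infer that the SAP contradicts the protocol throughout. Study drug means pitolisant or placebo (Protocol 5), so an AE that begins on double-blind placebo did not begin before study drug. For case A the protocol supports only the principle; case B is the literal conflict.
- A reader might infer that events disappear. All AEs are listed, with separate listings of serious AEs and of AEs leading to study discontinuation. The gap is in the summary tables.
- A reader might infer a demonstrated bias in favour of pitolisant. In the OLE tables the narrower rule can only lower counts, never raise them, but the amount may be zero. In the double-blind tables the direction is not fixed: a worsening carried back to an active arm would count against the drug.

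**Conclusion.** The point holds as a gap in the OLE definition. Applied as written, the start-date rule omits from the OLE summaries any earlier-onset AE that worsens on open-label pitolisant and keeps its original start date. The omission runs against the SAP's own general definition. For AEs with onset before any study drug it also runs against the letter of Protocol 9.4.3, and SAP 6.1 does not list it as a change from the protocol.

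The conclusion rests on one assumption, that at least some worsening AEs are kept as one record under the original date. Safety analyses are descriptive, and no primary or inferential result is affected. This is a minor point, worth correcting because the groups are small and the ex-placebo patients' first exposure falls in the OLE.

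**What to change.** In SAP 11.6.1 and in the OLE part of SAP 9.4, define OLE treatment-emergent AEs as AEs that start on or after the first OLE dose, together with ongoing AEs that worsen in severity or become serious on or after that dose. Keep the existing SAP 11.6.1 rule that brings AEs starting between the last double-blind dose and the first OLE dose into the OLE summaries. State that a worsening is identified either by a new AE record or by a dated change in severity, and say which of these the eCRF provides.

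The cost is a few lines of SAP text and the matching programming. There is one small downside. The documents show that severity is assessed for each AE, but not that changes in it are dated. If the eCRF holds a single undated severity per AE, ongoing AEs at OLE entry will need data clarification before the OLE lock.
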